Aim 1: To evaluate whether NIR-PBM stimulation can improve cognitive function in older adults with increased risk for Alzheimer's disease. Specifically, we plan to test whether 12 weeks of NIR stimulation, relative to sham, improves performance on memory (primary outcome) and executive function tasks sensitive to hippocampal and frontal brain function in older adults with increased risk for Alzheimer's disease. We hypothesize that NIR stimulation will result in greater improvement on tasks of H1.1) episodic memory and H1.2) executive function relative to sham. The primary outcome measure will be a spatial navigation task (ARENA), a human analogue to the Morris Water Maze¹⁷, that is sensitive to hippocampal function. A secondary cognitive outcome measure will be the executive function working memory composite score from the NIH Examiner battery known to be sensitive to frontal brain function.

Aim 2: To evaluate whether NIR-PBM intervention enhances brain function and connectivity in those at increased risk for Alzheimer's disease. We plan to test whether 12 weeks of NIR stimulation leads to enhanced markers of 31-P MRS ATP and rs-fMRI functional connectivity in older adults with increased risk for Alzheimer's disease. We hypothesize that: H2.1) NIR stimulation will produce pre-post increases in frontal and medial temporal brain markers of MRS ATP function and

H2.2) pre-post increases in functional connectivity in frontal and medial temporal lobe mediated resting state brain networks.

Exploratory Aim: To examine how baseline demographic, mood, vascular risk, genetic, and neuroimaging factors influence individual differences in cognitive outcome for NIR-PBM intervention. We plan to evaluate how baseline MRI white matter abnormalities, apolipoprotein E (APOE) ε4 status, and metabolic/vascular risk factors of hypertension and diabetes influence cognitive outcomes after 12 weeks of NIR stimulation. Additional factors include demographic (age, education, gender), mood status, and general processing efficiency. For this exploratory aim, we hypothesize that: HE.1) greater white matter lesion load on FLAIR MRI, HE.2) metabolic-vascular risk factors of hypertension and diabetes, and HE.3) APOE ε4 status will each predict poorer NIR-PBM outcomes in memory and executive function.

[figure not shown]
7. Research Plan

7.1 Design Overview.

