8.2. Randomization and Statistical Methods

8.2a. Randomization

Participants will be independently assigned to Sham and Active groups on a 1:1 ratio. Randomization will be stratified according to age and MoCA scores so as to prevent different average ages or cognitive status scores between the treatment groups (Active, Sham). Treatment assignment will be pseudorandomized in order to have comparable distributions of age and cognitive screening scores across Sham and Treatment interventions. Procedures will be followed so that group assignments are not available to individuals administering and scoring baseline/pre-intervention and post-intervention cognitive/mood data.

8.2b. Missingness and Intent to Treat

All data will be checked for missingness, out-of-range values, and distributional form (i.e., normality, homogeneity of variance). Decisions regarding use of parametric vs. nonparametric statistics will be based on the results of those analyses. Standard summary statistics will be provided for pre- and post-stimulation. Intent to treat analysis will be used to reduce selective attrition bias; participants who are unwilling/unable to continue with intervention will be encouraged to attend the post intervention testing, if possible. Thus, statistical analyses will be performed on two data sets: 1) on all subjects who were successfully screened, randomized and able to participate in at least 1 week of the assigned intervention, regardless of study completion (intention-to-treat analysis); and 2) on subjects who were successfully screened, randomized and able to complete at least 80% of the treatment assignment.

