8.3. Statistical Analyses

For hypotheses associated with Aims 1 (cognitive) and 2 (imaging), we plan to conduct linear mixed effects models and other potential analyses. For Aim 3, we are interested in predictors of treatment responses and will explore a variety of potential mediators and/or moderators including APOE-4 carrier status, vascular comorbidities (including white matter burden), mood/emotion, processing speed, and demographic variables. To examine confounders, we will directly adjust these variables as covariates in a linear mixed model. Additional analyses will be conducted as appropriate.

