All data will be checked for out-of-range values, and distributional forms (normality, homogeneity of variance). Decisions regarding parametric vs nonparametric statistics will be based on the results of those analyses. Standard summary statistics will be provided for pre, post- and follow-up time points. The intention-to-treat (ITT) principle will be applied whereby all randomized patients who complete the baseline assessment will be analyzed according to their assigned interventions. For studying the relationship between longitudinal outcomes and NIR stimulation effects, we will fit linear mixed effects models with subject specific random effects to account for the within subject correlation, using R software *lmer* package¹⁵⁸. Linear mixed model is robust against missing data if they are missing at random (MAR)¹⁵⁹. Baseline outcomes and covariates including age, sex, education, and other potential confounders (listed in Exploratory Aim 3) will be adjusted to take account for confounding effects. If multiple hypotheses are investigated simultaneously, multiple comparisons will be properly adjusted by using Benjamini-Hochberg correction¹⁶⁰. Below we describe how these statistical models fit the specific aims in this proposal.

Analyses for Aim 1: To test the hypothesis that the active NIR stimulation will result in greater pre-post intervention improvement in cognition (episodic memory, executive function) relative to the sham group, we will fit the following linear mixed model:

$$y_{ik} = \mu + \alpha_i + \beta \mathbb{I}(z_i = 1) + \sum_{l=0}^L \gamma_l x_{il} + \eta \mathbb{I}(k = 2) + \theta \mathbb{I}(z_i = 1, k = 2) + \varepsilon_{ik}, \alpha_i \sim N(0, \sigma_0^2), \varepsilon_{ik} \sim N(0, \sigma^2) \quad (1)$$

where y_{ik} is the outcome variable (e.g., ARENA score for Aim 1) for subject i and visit k ($k = 1$ for post-intervention and $k = 2$ for 3-month follow-up); μ is the intercept term; $\alpha_i \sim N(0, \sigma_0^2)$ is the random effect with variance term σ_0^2 for subject i ; z_i is the treatment indicator with $z_i = 0$ for sham group and $z_i = 1$ for active

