Analysis for Exploratory Aim 3: We want to further explore whether APOE $\varepsilon 4$ carrier status, vascular comorbidities, Fitzpatrick skin type questionnaires, processing speed, and mood are potentially confounders, moderators, or mediators. To examine confounders, we will directly adjust these variables as covariates in the linear mixed model in equation (1) and equation (2). A statistically significant covariate effect will imply the potential confounding roles of these variables. To examine moderators, we will include these variables and their interactions with the intervention effect (one variable at one time) in equation (1) and equation (2). A statistically significant interaction effect will imply the variable can be a moderator. To examine mediators, we will perform mediation analysis¹⁶¹⁻¹⁶². The mediation effects of these variables and their 95% confidence interval will be determined using the R *mediation* package¹⁶³.

For each of the specific aims listed above, we will further conduct exploratory analysis stratifying by sex, to examine its relevant biological effect. In other words, we will disaggregate the data by sex and evaluate the active stimulation effects for male and female, respectively.

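### The Aim 3 rule reads a significant covariate effect as a sign of potential confounding, but in a randomised trial it shows only that the variable is prognostic

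*SAP*

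**What the plan says.** The SAP, under Analysis for Exploratory Aim 3, asks whether APOE ε4 carrier status, "vascular comorbidities, Fitzpatrick skin type questionnaires, processing speed, and mood are potentially confounders, moderators, or mediators". Each role has its own method. Moderators are examined through interaction terms and mediators through a mediation analysis. For confounders, the variables enter equations (1) and (2) as covariates, and the result is read by this rule: "A statistically significant covariate effect will imply the potential confounding roles of these variables".

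Three other places bear on the point:

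- The opening paragraph of the SAP's Statistical Analysis section says that "other potential confounders (listed in Exploratory Aim 3) will be adjusted to take account for confounding effects". These variables are therefore in the models already.
- Protocol section 8.2a says "Participants will be independently assigned to Sham and Active groups on a 1:1 ratio", and then "Randomization will be stratified according to age and MoCA scores". Protocol section 7.2 names age, education and gender as the strata instead. On either account, none of the five Aim 3 variables is a stratification factor.
- Protocol section 8.3 says "To examine confounders, we will directly adjust these variables as covariates in a linear mixed model". It gives no significance rule.

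**The concern.** A confounder of the treatment effect must be related both to treatment and to outcome. The covariate's coefficient in equation (1) or (2) speaks only to the second link. Randomisation removes the first, except by chance. The evidence that would bear on confounding is the between-arm difference in the variable and the change in β when it is added. The SAP asks for neither.

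Followed as written, the rule gives the name of potential confounder to any variable that is prognostic enough to reach significance. The protocol's own hypotheses make this likely. It expects white matter lesion load, hypertension and diabetes, and APOE ε4 status to matter, in that they "will each predict poorer NIR-PBM outcomes in memory and executive function". If that expectation shows up as a main effect, Aim 3 would list such variables as potential confounders of a randomised comparison. At stake is how the Aim 3 table is read.

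**Working it through.** **Inputs.** From the SAP: 168 participants (84 per group), 5% alpha and 15% attrition. From Protocol section 7.2: two-tailed testing and 30% attrition. Assumed, because the documents do not give it: the partial correlation r between covariate and outcome, varied from 0 to 0.5.

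**Step 1: the plan's own figure.** The plan gives no figure for this rule, but its sample size feeds the check.
- The smallest design effect is d = 0.48. Normal approximation: 2 × (1.96 + 0.84)² / 0.48² gives 69 per arm after rounding up.
- 69 / 0.85 gives 82 per arm. The SAP states 84, so the figure reproduces to within two per arm.
- Evaluable sample: 168 × 0.85 = 142.8, about 143. At 30% attrition: 168 × 0.70 = 117.6, about 118.

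**Step 2: how often the rule flags a covariate unrelated to arm.** Fisher-z approximation at one visit: flag rate ≈ Φ(atanh(r) × √(n − 3) − 1.96). At r = 0 the two-sided test flags 5% by definition.

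| r | n = 143, √140 = 11.83 | Flag rate |
|---|---|---|
| 0 | – | 5% |
| 0.1 | 0.1003 × 11.83 − 1.96 = −0.77 | 22% |
| 0.2 | 0.2027 × 11.83 − 1.96 = 0.44 | 67% |
| 0.3 | 0.3095 × 11.83 − 1.96 = 1.70 | 96% |
| 0.4 | 0.4236 × 11.83 − 1.96 = 3.05 | >99% |

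At n = 118 and r = 0.3: 0.3095 × 10.72 − 1.96 = 1.36, or 91%. Strictly, each further covariate takes one more from n − 3, which lowers the rates slightly.

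**Step 3: simulation of the same rule.** Settings: 71 per arm, 1:1, one visit, outcome regressed on arm and covariate, covariate independent of arm, 5,000 runs per setting, true effect 0 or 0.48.
- With no treatment effect, flag rates were 5%, 22%, 66%, 96%, 99.9% and 100% at r = 0, 0.1, 0.2, 0.3, 0.4 and 0.5. With an effect of 0.48 they were 5%, 23%, 66%, 95%, 99.9% and 100%.
- The mean treatment effect, unadjusted or adjusted, was within 0.004 of the truth in every setting.
- Among flagged covariates, 4.3% to 5.6% also differed between arms at p < 0.05. That is the chance rate, so the flag carries no information about imbalance.
- Adjustment changed precision only. At r = 0.5 and no effect, the SD of the estimate fell from 0.170 to 0.146.

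**Step 4: what does move β.** In SD units, a chance imbalance shifts the β fitted without the variable by about r × imbalance. A covariate with r = 0.15 and a 0.4 SD imbalance shifts it by 0.15 × 0.4 = 0.06, yet is flagged only about 43% of the time (0.1511 × 11.83 − 1.96 = −0.17). One with r = 0.3 and no imbalance shifts it by nothing and is flagged 96% of the time. The flag follows prognostic strength, not influence on β.

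**The case against.** The strongest reply is that nothing turns on the flag. The SAP adjusts for the Aim 3 variables regardless, so the covariate set and the result for β are the same whatever the rule says. That stands, and it limits the point to the interpretation of an exploratory aim. A reader might infer that an imbalanced variable which escapes the flag goes uncorrected. The documents do not support that, because the variable remains in the model.

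Second, the SAP says only potential confounding, and association with outcome is one of the two conditions, so the sentence might pass as a loose screen. This stands in part. A reader might infer that the trial will declare its treatment effect confounded, and the text does not go that far. But the hedge does not let the criterion tell a prognostic variable from a confounder.

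Third, the percentages are the power to detect an assumed correlation, not a measure of bias. That is correct. What is left after adjustment for the baseline outcome, age, sex and education may be small, and at r = 0.1 the flag rate is only 22%. A Benjamini-Hochberg correction, if applied to these tests, would lower the rates. It would limit flags on variables unrelated to outcome (uncorrected, five independent ones give 1 − 0.95⁵ = 22.6% for at least one), but it would not change what a flag means.

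Fourth, dropout that differs by arm and depends on a covariate could create a real association with arm among those analysed. That stands as a limit on the illustration. The rule would not detect this either.

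Finally, a reader might infer that Protocol section 8.3 carries the same error. It does not: it announces adjustment and draws no inference from significance.

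**Conclusion.** The SAP sentence is wrong as written, and the severity is minor. A significant covariate effect in equation (1) or (2) shows a prognostic association. In a 1:1 randomised trial it does not indicate confounding, and the plan requires no check of imbalance or of change in β that would. The consequence is mislabelled results in exploratory Aim 3. The estimate and test of β do not depend on the rule.

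That conclusion follows from the text and needs no figures. The flag rates of about 5% to more than 99% for r from 0 to 0.4 are an illustration. They rest on assumed correlations, uncorrected 5% alpha, non-selective dropout and an evaluable sample of 142 to 143.

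**What to change.** Replace the one sentence in the SAP's Analysis for Exploratory Aim 3 with:

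> A significant covariate effect indicates a prognostic association with the outcome, not confounding. The influence of chance imbalance in each variable is described by the between-arm baseline difference and by β from the prespecified model fitted with and without that variable, using baseline values.

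The comparison is with the same model less one variable, not with a fully unadjusted β. Baseline values are named because processing speed and mood are measured again after the intervention and are also candidate mediators. The covariates in the SAP's equations carry no visit index, so baseline is the natural reading, but the SAP does not say so for these two.

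The cost is one sentence and one sensitivity refit per variable and outcome. With five variable groups, the six Aim 1 measures to which the SAP applies equation (1) and the four Aim 2 measures in its power section, at one score each, that is 5 × (6 + 4) = 50 refits, reported in an exploratory table. Sample size, alpha, the primary model, data collection and Protocol section 8.3 need no change.

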*Note that we are highly experienced in working with older adults who are identified as experiencing current major depression or other psychological disturbances or who perform below cutoff on standard cognitive screening measures. [name], at the UF site, is a boarded clinical neuropsychologist who has been working with this clinical population for over 30 years. Two Co-I's ([name], [name]) are experienced neurology clinicians. All are experienced with diagnosis and treatment of mood and cognitive disorders. Similar clinical expertise exists at the University of Arizona. Discussions will be held with individuals of concern and recommendations will be made to appropriate health care providers with permission of the participant and in line with standards of care. Specifics regarding how we address suicidality is described on page 19 of this protocol.

Sample Size, Attrition, Power, and Intent to

Treat. Our planned sample size includes 168 cognitively normal individuals (N=84 Active/N=84 Sham intervention). This sample size was determined directly from the effect sizes of our pilot data. Importantly, the study was powered to assess hypotheses proposed in Specific Aims 1 and 2, with 80% power. The vertical dash line in the figure to right shows the projected point at which 80% power will be achieved at $p=0.05$, two

tailed, relative to a sample size of the two treatment groups derived from the effect sizes of our pilot data. Based on our previous intervention studies with older adults, we anticipate a 30% attrition rate and up to 82 screen failures.

To account for screen failures and study attrition, we anticipate consenting up to 300 individuals.* Intent to treat analysis will be used to reduce selective attrition bias; participants who are unwilling/unable to complete the intervention will be encouraged to attend the post intervention testing. *(With informants, the number of involved individuals is doubled.)

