Title: Revitalizing Cognition in Older Adults at Risk for Alzheimer's Disease
using Near Infrared Photobiomodulation

[figure not shown]
8-1-2025

NCT04018092

STATISTICAL DESIGN AND POWER

Sample Size Determination/Power Analysis

The sample size calculation was based on our pilot results of all primary and secondary measures in Aim 1 and Aim 2. Here we use ARENA, our primary outcome that is being tested in Aim 1 (see H1.1) to illustrate the power calculation procedure. From our pilot data, the mean difference of ARENA score changes between active stimulation group ($n = 8$) and sham ($n = 5$) group was 0.58. Based on a pooled standard deviation of 0.55, the standardized effect size (Cohen's d) is $d=1.06$. Similarly, we calculated the standardized effect sizes of our secondary outcome variables, including working memory (H1.2, $d=0.67$); prefrontal cortex ATP (H2.1, $d=0.48$); temporal lobe ATP (H2.1, $d=0.5$); prefrontal cortex connectivity (H2.2, $d=1.3$); and temporal lobe connectivity (H2.2, $d=1.1$). Based on our experience of 10% attrition in a clinical trial with three months of intervention for the ACT study (MPI: [name]; PI UA Field Site: [name]) that is currently underway at the UF and UA field sites, we conservatively assumed 15% attrition in the power calculations for the current proposal. At 5% alpha level and assuming the 15% attrition rate, the power trajectories for different measures with respect to number of samples per treatment group are shown in the above figure. In order to guarantee that all these primary and secondary measures have more than 80% power, we plan to enroll a total of 168 participants (84 per group, shown as the dashed line in the above figure). This large sample size will also ensure sufficient statistical power for the exploratory analysis of Aim 3, where we will examine potential mediators and moderators in relation to the intervention response. Note that we are powering the study based on a 2-week session and the actual effect sizes (from a 12-week NIR stimulation session) will likely exceed these minimal estimates.

Statistical Analysis

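### The SAP examines the effect of sex by separate male and female analyses, with no treatment-by-sex interaction or estimate of the difference

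*SAP*

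**What the plan says.** The closing paragraph of the SAP adds, for every aim, an exploratory analysis stratified by sex, with the purpose of examining the biological effect of sex. The only method given is: "we will disaggregate the data by sex and evaluate the active stimulation effects for male and female, respectively". It states no interaction term, no estimate of the male-female difference and no rule for reading the two results together. In equations (1) and (2) sex appears only as a main-effect covariate.

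The paragraph just before it (SAP, Analysis for Exploratory Aim 3) handles moderators differently: "To examine moderators, we will include these variables and their interactions with the intervention effect (one variable at one time"), and a significant interaction is taken as a sign of moderation. The variables it covers are APOE ε4, vascular comorbidity, skin type, processing speed and mood. Sex is not among them.

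The protocol does put sex with the moderators. The Exploratory Aim in section 6 includes gender among its additional factors, section 7.5.3 includes sex among the factors that might affect response, and section 8.3 counts demographic variables among the possible mediators or moderators. None of these sections writes down a sex interaction model.

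**The concern.** Whether treatment works differently in men and women is a question about a difference between two effects. Two separate analyses give two estimates and two p-values but no test or interval for that difference. If one sex reaches significance and the other does not, it is easy to conclude that the treatment works in one sex only. That pattern is common by chance when power within each sex is moderate, because each sex has only about half the participants. At stake is a misleading secondary message about sex, most of all for the outcomes with the smaller assumed effects. The primary and secondary treatment tests are not affected.

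**Working it through.** **Inputs**
- Alpha and attrition: "At 5% alpha level and assuming the 15% attrition rate" (SAP, Sample Size Determination/Power Analysis). The tests are two-sided: "80% power will be achieved at $p=0.05$, two" tailed (Protocol 7.2).
- Power target: "In order to guarantee that all these primary and secondary measures have more than 80% power" (SAP).
- Size: "we plan to enroll a total of 168 participants (84 per group") (SAP). Allocation: "Participants will be independently assigned to Sham and Active groups on a 1:1 ratio" (Protocol 8.2a).
- Attrition: "we conservatively assumed 15% attrition in the power calculations for the current proposal" (SAP). Protocol 7.2 anticipates 30%, used below as a sensitivity value.
- Effect sizes (SAP): ARENA 1.06, working memory 0.67, prefrontal ATP 0.48, temporal ATP 0.5, prefrontal connectivity 1.3, temporal connectivity 1.1.
- Sex split: Protocol 7.2 hopes for equal numbers. A 30% share of men is my assumption for sensitivity.

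**Step 1. Reproduce the plan's sample size.** The smallest effect, d = 0.48, drives it. By the normal approximation, n per arm = 2 × (1.960 + 0.842)² / 0.48² = 68.1, so 69. Dividing by 0.85 gives 81.2, so 82. The noncentral t gives 70, and 70 / 0.85 = 82.4, so 83. The plan's 84 is within 2 per arm. With 84 × 0.85 = 71.4 per arm, power at d = 0.48 is 0.81 to 0.82. The inputs are therefore read correctly.

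**Step 2. Size within each sex.** 168 × 0.85 / 4 = 35.7 per arm per sex. The standard error of the effect within one sex, in SD units, is √(2 / 35.7) = 0.237.

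**Step 3. Chance of discordant significance when the true effects are equal.** Power p within each sex comes from the two-sample noncentral t with noncentrality d / 0.237. For equal halves, P(exactly one sex significant) = 2p(1 − p). For unequal splits it is p_m(1 − p_f) + p_f(1 − p_m). Results use unrounded powers.

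| Outcome | d | Power within each sex | Exactly one sex significant |
|---|---|---|---|
| Prefrontal ATP | 0.48 | 51.6% | 49.9% |
| Temporal ATP | 0.50 | 54.9% | 49.5% |
| Working memory | 0.67 | 79.7% | 32.3% |
| ARENA (primary) | 1.06 | 99.3% | 1.4% |
| Temporal connectivity | 1.1 | 99.6% | 0.9% |
| Prefrontal connectivity | 1.3 | about 100% | 0.1% |
| No effect in either sex | 0 | 5.0% | 9.5% |

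**Step 4. Sensitivity.**

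| Scenario | d = 0.48 | d = 0.67 | ARENA, d = 1.06 |
|---|---|---|---|
| 30% attrition, equal sexes | 49% | 41% | 4% |
| 15% attrition, 30% men | 55% | 44% | 8% |
| 30% attrition, 30% men | 53% | 51% | 14% |

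**Step 5. The interaction test.** Its standard error is √2 × 0.237 = 0.335 SD. In simulation (40,000 trials per effect size, 36 per arm per sex, equal true effects) it was significant in 4.9% to 5.2% of trials at d = 0, 0.48, 0.67 and 1.06. In the same trials exactly one sex was significant in 9.3%, 50.0%, 31.8% and 1.3%, which agrees with step 3.

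**Step 6. What the interaction can detect.** The sex difference detectable with 80% power is (1.960 + 0.842) × 0.335 = 0.94 SD. Power is about 30% for a difference of 0.48 SD and 52% for 0.67 SD.

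**The case against.** - **The SAP does not say that significance will be compared between the sexes.** This is correct. A reader might infer such a rule from the word that closes the sentence on male and female effects, but the text commits only to evaluating the effect in each. The discordance figures are the error rates of that inferred reading.
- **A reader might extend the 50% to every measure, the primary outcome included.** The SAP's own effect sizes do not support this. It fits only the two ATP measures. ARENA would come near one half only if its true effect were about 0.4 to 0.5. That is conceivable, since 1.06 comes from 13 pilot participants, but it is an assumption.
- **The planned output is not useless for the question.** The SAP promises a point estimate and confidence interval from these models. Men and women are independent samples, so the difference can be derived with SE = √(SE_m² + SE_f²). What is missing is a commitment to report it.
- **Separate fits are a legitimate modelling choice.** Letting covariate slopes and variances differ by sex costs some precision but is not an error.
- **Multiplicity.** The SAP plans a Benjamini-Hochberg correction when several hypotheses are tested together. Whether this reaches the sex strata is unclear, and the figures above are unadjusted.
- **The analysis is exploratory and the interaction has low power.** Both are true. They limit the weight of the point, and they are also a reason to report an interval for the difference, which would show how little the trial can say about sex.

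The gap in specification survives these objections, as does the mismatch between the SAP's moderator list and the protocol.

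**Conclusion.** The point holds in a limited, conditional form. The SAP studies the effect of sex without an interaction or a difference estimate, although it applies interactions to its other moderators and the protocol treats sex as one of the factors of interest. Should significance be compared across the sexes, equal effects would look different in about 50% of trials for ATP, 32% for working memory and about 1% or less for ARENA and connectivity, against about 5% for an interaction test.

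These figures rest on 15% attrition, equal numbers of men and women, balanced arms within each sex, unadjusted two-sided 5% tests, the SAP's pilot effect sizes, and a two-sample comparison standing in for the mixed model. Balance within sex is itself uncertain, because Protocol 7.2 stratifies randomization by age, education and gender, whereas 8.2a stratifies by age and MoCA. The documents do not support saying that the trial will judge sex differences by comparing p-values, or that the primary outcome is exposed to a false finding in half of trials. This is a free improvement to an exploratory analysis.

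**What to change.** Add sex to the SAP's list of moderators, in line with the protocol. Replace the split with one model on all participants that includes treatment by sex, and in equation (1) also treatment by visit by sex with its lower-order terms. Report the interaction estimate with its 95% CI, take the male and female effects as contrasts from the same model, and state that no conclusion about a sex difference will be drawn from within-sex p-values. Keep the analysis exploratory, say whether the Benjamini-Hochberg correction covers it, and state that it has 80% power only for a sex difference of about 0.94 SD.

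The cost is SAP wording. No participants, visits or data are added, and sex-specific estimates are still produced.
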